11.1 Study Hypotheses

This pilot study is designed to test the following hypotheses:

- (1) The proportion of the high-risk HPV infection among individuals selected for oral rinse collection will be similar to the proportion predicted by the risk factor model;
- (2) Baseline study procedures will be feasible and acceptable to dental practice staff and patients;
- (3) The distribution of demographic and behavioral risk factors in the study population will be similar to the US population; and
- (4) Participants will be compliant with follow-up study procedures, including the blood draw, oral cancer screening examination, second oral rinse specimen collection and detailed oral cancer risk factor survey (Appendix J); and
- (5) Arranging and conducting the procedures will be feasible for RC and dental practice staff.

The study will determine whether or not oral HPV detection can be used to identify individuals in a dental practice who are at high-risk for HPV-associated oral cancer and who should be targeted for referral and screening for oral cancer.

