11.2 Sample Size Considerations

The sample size for this pilot study is based upon a dichotomous outcome in which participating patients are categorized as low-risk versus high-risk for oral high-risk HPV infection. Based upon our risk model derived from 5,500 individuals who are representative of the US population (NHANES), we expect 30% of the study population to be categorized as high-risk. A two-sided test of proportions with a type 1 error of 0.05 indicates that a pilot study with 1,000 individuals will have 90% power to detect a 5% or greater difference in the proportion of the study population that is categorized as high-risk. The ability to enroll a sample size of 1,000 will also provide assurance that a study with a large sample size is feasible in the National Dental PBRN.

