To accomplish secondary objective (2) the distribution of the demographic and behavioral variables in the study population will be compared to the weighted distribution of the same factors in the US population per NHANES. In this analysis, the distribution of the populations into deciles of risk will be represented in an $n \times k$ table where n represents the two populations and k the deciles of risk. The distribution will be compared by chi square test with nine degrees of freedom. The distribution of each variable in the two populations will also be compared in univariate analysis. Successful completion of this pilot will therefore: (1) assess patient acceptability of the procedures; (2) provide training to study personnel and assess the feasibility of incorporating the study procedures into clinical practice; and (3) inform the point estimates and models used for sample size determination for a future larger study to ensure that the estimate of 60,000 screened individuals is appropriate.

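### Section 11.3 compares ordered risk deciles with an unordered 9-df chi-square; a 1-df trend test and the mean decile difference with its 95% CI should be added beside it

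*Protocol*

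**What the plan says.** Hypothesis (3) in Protocol Section 11.1 reads: "The distribution of demographic and behavioral risk factors in the study population will be similar to the US population". Section 11.3 addresses it under secondary objective (2). It lays out a table "where n represents the two populations and k the deciles of risk" and continues: "The distribution will be compared by chi square test with nine degrees of freedom". Each risk factor is also compared separately between the two populations. No trend test, rank test or estimate of shift across the deciles is named.

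A second comparison uses the same ordering. Section 11.2 says "we expect 30% of the study population to be categorized as high-risk" and claims "90% power to detect a 5% or greater difference in the proportion of the study population that is categorized as high-risk", from a two-sided test of proportions at 0.05 with 1,000 patients. Section 11.3 then lists the number of patients in the top three deciles as an outcome under the primary objective, and says that this number will also inform on how risk factors are distributed.

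**The concern.** The deciles come from a risk score, so decile 10 means more predicted risk than decile 1. The plan relies on that order when it selects the top three deciles for the oral rinse. A Pearson chi-square on the 2 x 10 table gives the same p-value if the deciles are shuffled. When the dental population is shifted as a whole towards higher or lower risk, the signal lies along one direction, and testing it on nine degrees of freedom costs power.

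The p-value also does not say which way the population differs or by how much. Section 11.3 wants the pilot to inform the models behind the estimate of 60,000 people to be screened. An estimated shift with an interval serves that purpose better than an omnibus p-value.

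**Working it through.** **Inputs.** Study n1 = 1,000; two-sided 0.05; reference 30% in the top three deciles; difference 5 points; NHANES n2 = 5,500 (all Section 11.2). Section 11.3 states no alpha for the chi-square, so 0.05 is assumed. The reference deciles hold q_j = 10% each. The shape of any shift is not given, so several are assumed. Subjects are treated as independent.

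**The plan's own figures.**
- Degrees of freedom: (2 - 1)(10 - 1) = 9, as stated.
- Two-sample test, 35% against 30%: pooled p = (350 + 1,650)/6,500 = 0.3077. The null SE is 0.01587 and the alternative SE is 0.01630. z = (0.05 - 1.96 x 0.01587)/0.01630 = 1.16, so power is 87.7%. For 25% against 30% it is 90.1%.
- One-sample test against 30%, upward: (0.05 - 1.96 x 0.01449)/0.01508 = 1.43, so power is 92.4% (exact binomial 91.3%).
- The stated 90% is therefore reproduced to within about 2 points upward.

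**Power of the two decile tests.** Let κ = n1·n2/(n1 + n2) = 846.2, let p_j be the study proportions, p̄_j the pooled proportions and s_j = 1 to 10 the scores.
- 9-df noncentrality: λ9 = κ Σ (p_j - q_j)²/p̄_j, critical value 16.92.
- 1-df trend noncentrality: λ1 = κ (Σ s_j(p_j - q_j))²/Var(s), critical value 3.84.

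*Step at the cut, 30% to 35%.* Each of the top three deciles gains 0.05/3 and each of the other seven loses 0.05/7.
- λ9 = 846.2 x (3 x 0.0002778/0.10256 + 7 x 0.0000510/0.09890) = 9.93, power 56.0%.
- Mean decile difference = 27 x 0.01667 - 28 x 0.00714 = 0.25. λ1 = 846.2 x 0.25²/8.30 = 6.37, power 71.4%.

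*Normal shift, 30% to 35%.* The shift is z(0.70) - z(0.65) = 0.139 SD.
- λ9 = 15.69, power 80.1%.
- Mean decile difference 0.386. λ1 = 846.2 x 0.386²/8.26, about 15.2, power 97.4%.

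All shapes, 1,000 against 5,500:

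| Shape | Up, 9-df | Up, trend | Loss (points) | Loss downward (points) |
|---|---|---|---|---|
| Linear | 80.6% | 97.8% | 17 | 17 |
| Exponential tilt | 77.6% | 97.1% | 20 | 15 |
| Normal shift | 80.1% | 97.4% | 17 | 12 |
| Step at the cut | 56.0% | 71.4% | 15 | 14 |

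The loss is 12 to 20 points. A simulation of the linear upward case (20,000 tables) gave 81.1% against 97.9%.

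**Sensitivity.**
- NHANES deciles treated as fixed: smooth shifts lose about 7 to 13 points.
- Smaller smooth shifts lose more: normal shift to 33%, 32.7% against 66.1%.
- A common design effect of 2 (assumption, for survey weighting and clustering): linear shift, 45% against 80%.
- Reversals, simulated: 5 points all in decile 10, 92% (9-df) against 85% (trend); all in decile 8, 92% against 52%; a U-shaped change, 84% against 6%.

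**Against the whole plan.** The two-sample proportion test at the top-three-decile cut has 87.7% power upward. The trend test adds 97.4 - 87.7 = 9.7 points for the normal shift to 35%, and 66.1 - 47.5 = 18.6 points for the normal shift to 33%. For the step it adds nothing (71.4% against 87.7%).

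**The case against.** The strongest reply is that the plan already has a directional 1-df comparison. Section 11.2 specifies a two-sided test for "to detect a 5% or greater difference in the proportion of the study population that is categorized as high-risk", and Section 11.3 ties the count in that group to the distribution of risk factors. This stands, and it reduces the practical loss from 12-20 points to about 10 for a smooth upward 5-point shift. It does not remove the point. That outcome sits under the primary objective, it uses one cut only, it cannot see movement within the lower seven deciles, and it is weaker than a trend test for smooth shifts.

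A second reply is that hypothesis (3) concerns the distribution as a whole, which an omnibus test matches. This also stands. A trend test leading alone would miss U-shaped or single-decile differences that the 9-df test detects, so the documents give no ground for replacing the chi-square.

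A reader might also infer that a weak test favours the sponsor, because a non-significant result would be declared similarity. The protocol says only that the distributions will be compared. It states neither that rule nor a similarity margin. If such a rule were used, a trend test would not cure it; an interval judged against a stated margin would.

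Finally, extra detail may stand in the SAP, which is not at hand. The protocol nevertheless names this test for the decile table, so the choice can be assessed as written.

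**Conclusion.** The point holds as an inexpensive improvement, not as an error. The chi-square is valid and its degrees of freedom are right, but it ignores the order of the deciles and reports no direction or size. The 12 to 20 point loss against a trend test applies under stated conditions: a monotone change, the plan's 5-point difference, about 5,500 independent NHANES subjects and two-sided 0.05. It is not a general figure: it falls to about 7-13 points for smooth shifts against a fixed reference, grows for smaller smooth shifts, and reverses for single-decile or U-shaped changes. With the plan's own proportion test counted, the net gain in power is about 10 points for a smooth upward 5-point shift, about 19 at 33%, and none for a step at the cut. The more lasting benefit is an estimate of the shift with its interval. The documents do not support the stronger readings that the test is invalid or that the plan will take non-significance as proof of similarity.

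**What to change.** In Section 11.3, keep the 9-df chi-square. Add beside it the 1-df linear trend test (Cochran-Armitage, or linear-by-linear) over decile scores 1 to 10, or a Wilcoxon test on the uncut model score. Report it with the mean decile difference between the study and NHANES and its 95% CI. Under the independence assumption the CI half-width would be about 1.96 x sqrt(8.25 x (1/1,000 + 1/5,500)) = 0.19 deciles. State that non-significance of either test will not be read as similarity.

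The cost is one or two sentences and one more line of analysis on data already collected, with no extra patients or procedures. The small downside is a second p-value for a secondary objective of a pilot.

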12 SOURCE DOCUMENTS AND ACCESS TO SOURCE DATA/DOCUMENTS

Each participating practitioner will maintain appropriate medical and research records for this study, using the principles of good clinical practice and complying with regulatory and institutional requirements for the protection of confidentiality of patients. Each practitioner will permit authorized representatives of NIDCR and regulatory agencies to examine (and when required by applicable law, to copy) research records for the purposes of quality assurance (QA) reviews, audits, and evaluation of the study safety, progress and data validity.

The following clinical records will be considered source documents where they are used to complete CRFs: clinical and office charts, memoranda, and recorded data from automated instruments.

The following eCRFs or portions of eCRFs will be considered source documents, as it is not expected that all patients' clinical charts would contain the exact information collected on these eCRFs: Eligibility Screening, Consent Comprehension, Contact Information, the electronic oral HPV risk factor survey (Appendix C), oral rinse sample collection, the electronic oral cancer risk factor survey (Appendix J), and the provider survey (Appendix P).

All study source documents must be maintained in a secure manner, and practice personnel and network personnel will have access to source documents. Study source documents may include clinical records and as such are subject to HIPAA regulations. These records will be subject to examination and copying as stated elsewhere in this section.

13 QUALITY CONTROL AND QUALITY ASSURANCE

A high-level Quality Management Plan is detailed in Appendix L. In brief, QA and quality control (QC) activities will be implemented for each key study activity, including practitioner recruitment, training, and enrollment; patient screening and enrollment; patient follow-up; data collection; biospecimen collection, storage, shipping, tracking, and processing; and data analysis and interpretation. The study's MOP will provide further detail to operationalize study QA/QC procedures.

For the QA/QC activities associated with data collection and processing, OSU will develop a Data Management Plan (DMP) (outline provided in Appendix M) in collaboration with Westat and/or NIDCR in which the specific data QA/QC procedures will be provided. The procedures will include the development of automatic data quality checks in the web-based application and the processes related to the data manual review, discrepancy management, delinquent data handling, data updates, data verification and approval, and database audit. A work instruction will be provided to the RCs at the RAS with the specified tasks, timelines of completing the tasks, roles and responsibilities. The OSU Clinical Data Manager will work with the RCs to ensure that all procedures are followed and that the data are checked according to the validation requirements specified in the DMP. The OSU Clinical Data Manager will verify the completion of data entry and clarifications by running monitoring reports. Once confirmed that the data entry are complete and the data are verified and approved for accuracy, the database will be locked for final analysis. During the study period, when interim data analysis is needed, the OSU Clinical Data Manager will coordinate the activities with the RCs and the Statistician. The interim datasets will be provided with the data collected as of the specified date. The data in those datasets will be cleaned if possible but may contain pending issues that will be provided to the Statistician if requested. The datasets will be provided to the Statistician via secure data transfer method.

14 ETHICS/PROTECTION OF HUMAN SUBJECTS

14.1 Ethical Standard

The investigator will ensure that this study is conducted in full conformity with the principles set forth in The Belmont Report: Ethical Principles and Guidelines for the Protection of Human Subjects of Research, as drafted by the US National Commission for the Protection of Human Subjects of Biomedical and Behavioral Research (April 18, 1979) and codified in 45 CFR Part 46.

14.2 Institutional Review Board

It is recognized that this protocol must receive the approval of many unique IRBs, and each may have different criteria for patient informed consent. Therefore, different regions may have slightly varied informed consent procedures and documents. For the purposes of this minimal risk, non-intervention study, the following will be considered acceptable by the study investigators, at the discretion of the responsible IRB: electronic consent for the initial (screening) phase of the study, followed by telephone (verbal) consent for the final (follow-up) phase of the study.

The protocol, informed consent documents, appendices and recruitment materials will be submitted to the IRB for review and approval. Approval of both the protocol and the consent documents must be obtained before any participant is enrolled. Any amendment to the protocol will require review and approval by the IRB before the changes are implemented in the study.

14.3 Informed Consent Process

14.3.1 General Information

Informed consent is a process that is initiated prior to the individual agreeing to participate in the study and continues throughout study participation. Protocols for the informed consent process will vary across practitioners, practices and regions, and will be determined by individual IRBs.

In general, an extensive description of risks and possible benefits of study participation will be provided to patients electronically (initial study visit) or over the phone (follow-up study). All study participants will receive a copy of the Oral HPV FAQ documents (Appendix K) and a hard copy of the informed consent form at the time of enrollment. Due to the variability of informed consent templates and IRB requirements across collaborating practices and regions, the electronic and hard copy consents will not be identical. The language in the electronic consent is universal and administered to every study participant via the study web-application; the patient will read this electronic form and indicate consent electronically. Afterward, region-specific consent procedures will be followed and may include additional verbal and/or written consent procedures. Some IRBs may require study participants to sign a paper informed consent document along with their electronic agreement. For all regions, a region-specific

paper consent document will be provided to each participant for their records after consent procedures have been completed.

All consent forms and scripts will be IRB-approved. The participant is required to read and review the document or have the document read to him or her, and the investigator or designee will answer any questions that may arise. The participant will indicate agreement to participate in the study prior to any study-related assessments or procedures. Participants will be given the opportunity to discuss the study with their surrogates or think about it prior to agreeing to participate. They may withdraw consent at any time throughout the course of the study. The rights and welfare of the participants will be protected by emphasizing to them that the quality of their clinical care will not be adversely affected if they decline to participate in this study.

The consent process will be documented in the research record. Study procedures, including patient informed consent will be tracked by means of a web-based computer application. Practitioners will be consented by RCs according to regional IRB requirements. Criteria for consent and results of consent process will be tracked administratively.

14.3.2 Oral HPV Screening Consent Process

The oral HPV screening phase of this study has been determined to be low-risk and therefore electronic consent, administered on a tablet computer/web-application, is appropriate for the first consent process. Appropriate waivers of consent documentation should be obtained by the practitioner's governing IRB, if required.

1. The web application will verify patient eligibility.
2. The consenting individual will inform eligible patients that they may ask questions before, during and after the electronic consent process.
3. The web application will show an IRB-approved Electronic Study Summary. This page will explain the study rationale, procedures, risks and benefits to the patient; See Appendix A: *Electronic Study Summary, Part I (Oral HPV Screening)*.
4. The web application will administer a three-question survey to assess the patient's comprehension of the study.
5. After reviewing the study summary and completing the comprehension survey, the patient may indicate their agreement to participate electronically.
6. A hard copy, IRB-approved Informed Consent Form will be provided to a patient at the time of enrollment. See Appendix B: *Informed Consent Form, Part I (Oral HPV Screening)*.

14.3.3 Oral Cancer Screening Follow-up Study Consent Process

Consent for the follow-up portion of this study for those with positive high-risk HPV results must be carried out via telephone by the RC. Appropriate waivers of consent documentation and approval of the telephone consent script should be obtained by the practitioner's governing IRB, if required. See Appendix H: *Telephone Consent Script, Part II (Oral Cancer*

Screening Follow-up Study) and Appendix I: *Informed Consent Form, Part II (Oral Cancer Screening Follow-up Study)*.

14.4 Exclusion of Women, Minorities, and Children (Special Populations)

All men and women between the ages of 30-69 years will be eligible to enroll in this study. Individuals under the age of 30 years are excluded from participation because data from the US population indicate this age group is at extremely low risk for high-risk oral HPV infection and oral cancer.

14.5 Participant Confidentiality

Participant confidentiality is strictly held in trust by the investigators, study staff, and the sponsor(s) and their agents. This confidentiality is extended to cover testing of biological samples in addition to any study information relating to participants.

For a majority of participating patients, the data will be collected without patient reporting of identifiers (e.g., will be anonymous).

The study protocol, documentation, data, and all other information generated will be held in strict confidence. No information concerning the study or the data will be released to any unauthorized third party without prior written approval of the sponsor.

Patients will be assigned a unique identification number, which will be used to maintain study records and organize data transcripts. A file linking patients' names with their unique identification number will be kept in a password-protected file on the CC's computer, separate from all other research records.

The study monitor or other authorized representatives of the sponsor may inspect all study documents and records required to be maintained by the investigator, including but not limited to, dental and medical records (office, clinic, or hospital) for the study participants. The clinical study practitioners will permit access to such records.

The tablet computer and web-application are password-protected and all data are encrypted. Questionnaire response data will not be available to local care providers. Study data will be stored on secure servers at OSU and Westat. To protect the confidentiality of the data, a Certificate of Confidentiality will be obtained by the US Federal Government to protect data from release to any party, except with the expressed consent of the study patient. Certificates of Confidentiality were designed to protect patients who participate in studies in which collection of sensitive, stigmatized or illegal behavioral data is necessary. Although administered on a tablet computer to enhance confidentiality of survey administration for the study participant, the software will be a web-based application accessible on any computer. The consent form will include language compliant with HIPAA regulations.

14.6 Future Use of Stored Specimens and Other Identifiable Data

Participants in this study will be asked for authorization to have their oral rinse and blood samples stored in a freezer and potentially used for future research. The samples will be stored at OSU for 10 years, and will only be used by the investigator of this study for research on HPV and how mouth and throat cancers develop. Testing may include analysis of genes that may affect risk of HPV infection, inflammation or cancer. The data from genetic testing will be stored electronically in a secure data repository and will be made available for secondary research.

15 DATA HANDLING AND RECORD KEEPING

The investigators are responsible for ensuring the accuracy, completeness, legibility, and timeliness of the data reported. All source documents should be completed in a neat, legible manner to ensure accurate interpretation of data. The investigators will maintain adequate case histories of study participants, including accurate CRFs, and source documentation. The Data Management Plan Outline is detailed in Appendix M.

Only study personnel (i.e., GPI, SPI, Co-I's, RCs, and CC personnel) and clinical site monitors will have access to the study data elements in the study database as described in Section 15.3 Types of Data. Study personnel will include those who are on the approved IRB study protocol. All study personnel will have completed the required training elements for human subjects research certification.

